10.2.4 Other safety topics of interest

The other safety topics of interest for this study include:

- Infections (serious, fungal, opportunistic and tuberculosis)
- Malignancies
- Major adverse cardiac events (MACE)
- Neutropenia
- Suicidal Ideation and Behavior (SIB) Inflammatory bowel disease
- Hypersensitivity (including anaphylaxis)
- Hepatic events and drug-induced liver injury (DILI)

The analyses produced for the above TEAE are based on the specifications described in the BKZ safety topic of interest document version from Apr-2021.

The incidence of other safety topics of interest will be summarized by MedDRA system organ class, high level term, and PT. EAIR with associated 95% CI and the EAER will be included in the summary tables.

Separate tables will be created to summarize the incidence of each of the above AEs (unless otherwise specified) per 100 subject-years, by SOC, HLT, and PT. A listing will also be created.

10.2.4.1 Infections (serious, opportunistic, fungal and TB)

Serious infections will be identified based on MedDRA classification (SOC “Infections and infestations”) using the “Any SAE” table. A separate table does not need to be produced to summarize these events.

- Fungal infections will be summarized in a stand-alone table. The table will include all TEAEs (serious and non-serious) which code into the High-Level Group Term (HLGT) “Fungal infectious disorders”.
- Opportunistic infections (including tuberculosis) will be summarized in a stand-alone table and will include all opportunistic infection TEAEs identified as per the UCB-defined search criteria which were adjudicated as opportunistic infections (refer to [Section 12.2](#) for further details on the process for identifying opportunistic infections).

10.2.4.2 Malignancies

Two tables will be created on malignancies:

- One table will be based on the criteria SMQ= “Malignant or unspecified tumors (SMQ)”.
- One table will be based on the criteria SMQ= “Malignant tumors (SMQ)”.

SMQ search will include all TEAEs which code to a PT included in the Scope=Narrow group within each SMQ.

Note that the events included in the “Malignancies” table will be a subset of the events included in the “Malignancies (including unspecified)” table. While the “Malignant tumors (SMQ)” is most relevant, “Malignant or unspecified tumors (SMQ)” must be reviewed for potential malignancies.

The output tables will include 2 different overall incidence rows:

- The first overall incidence row will summarize “Any Malignancy” and this row will summarize the incidence of all AEs flagged for inclusion in the table (using the appropriate SMQ depending on the table), regardless of the High Level Term (HLT) it codes to.
- The second overall incidence row will summarize “Any Malignancy excluding non-melanomic skin cancers HLT” and this row will summarize the incidence of AEs flagged for inclusion in the table (using the appropriate SMQ depending on the table), excluding those which code to an HLT of “skin neoplasms malignant and unspecified (excl melanoma)”.

10.2.4.3 Major adverse cardiac events (MACE)

Major adverse cardiac events will be presented in a table. The classification of an event as MACE is determined by external cardiovascular event adjudication committee.

Extended MACE events will be presented in a separate table and listing. All events which are classified by the adjudication committee as any of the following events types will be considered an extended MACE event.

Table 10–1: Type of Extended MACE events

Event Type Code	Event Type
1	Non-Fatal Myocardial Infarction (MI)
2	Non-Fatal Stroke: hemorrhagic
3	Non-Fatal Stroke: ischemic
4	Non-Fatal Stroke: embolic
5	Non-Fatal Stroke: undeterminable
6	Hospitalization or ER for Unstable Angina with urgent revascularization
8	Hospitalization for Heart Failure
10	Coronary Revascularization Procedures (eg, percutaneous coronary intervention, coronary artery bypass grafting)
11	Urgent Revascularization Procedures (ie, due to symptoms of brain ischemia or pending infarction)
18	Death due to Myocardial Infarction (MI)
19	Death due to Stroke
20	Sudden Cardiac Death

Event Type Code	Event Type
21	Other CV Death (eg, heart failure, pulmonary embolism, cardiovascular procedure-related)
22	Cardiovascular: Undetermined Cause of Death (ie, cause of death unknown)

A separate table and listing will present the adjudicated cardiovascular events by type. For each cardiovascular event type (24 in all, for full list refer to Bimekizumab-Event-Adjudication-Committee-Analysis- Plan), the individual PTs which fall within each event type will be summarized.

Additionally, a listing of all events identified for potential review by the cardiovascular event adjudication committee will be produced. This listing will indicate whether each event was escalated to the committee for formal review/adjudication.

10.2.4.4 Neutropenia

The table on neutropenia will be based on the following PTs (regardless of seriousness):

- Autoimmune neutropenia
- Band neutrophil count decreased
- Cyclic neutropenia
- Febrile neutropenia
- Idiopathic neutropenia
- Neutropenia
- Neutropenic infection
- Neutropenic sepsis
- Neutrophil count decreased

10.2.4.5 Suicidal Ideation and Behavior Neuropsychiatric events

An external neuropsychiatric adjudication committee will evaluate potential neuropsychiatric events and determine whether any of those events were associated with suicidal ideation and behavior (SIB). If an event is adjudicated as SIB, further information will be provided. A table and a listing for SIB events as determined by the adjudication committee will be produced.

A separate table will present the adjudicated neuropsychiatric events by type. For each neuropsychiatric event type (6 total), the individual PTs which fall within each event type will be summarized. It will include events adjudicated as SIB and events adjudicated as non-suicidal. Note that the event type Suicidal ideation can be classified as either SIB or non-suicidal.

Additionally, a listing of all events identified for potential review by the neuropsychiatric adjudication committee will be produced. This listing will indicate whether each event was escalated to the committee for formal review/adjudication. A separate listing will also be produced to summarize the adjudicated results of all events escalated to the full committee.

10.2.4.6 Inflammatory bowel disease

An external inflammatory bowel disease (IBD) adjudication committee will evaluate potential IBD events and will classify each one as follows:

- Event Type Code 1: Possible IBD – Crohn’s Disease
- Event Type Code 2: Probable IBD – Crohn’s Disease
- Event Type Code 3: Definite IBD – Crohn’s Disease
- Event Type Code 4: Possible IBD – Ulcerative Colitis
- Event Type Code 5: Probable IBD – Ulcerative Colitis
- Event Type Code 6: Definite IBD – Ulcerative Colitis
- Event Type Code 7: Possible IBD – Unclassified
- Event Type Code 8: Probable IBD – Unclassified
- Event Type Code 9: Definite IBD – Unclassified
- Event Type Code 10: Symptoms not consistent with IBD
- Event Type Code 11: Possible Inflammatory Bowel Disease – Microscopic Colitis
- Event Type Code 12: Probable Inflammatory Bowel Disease – Microscopic Colitis
- Event Type Code 13: Definite Inflammatory Bowel Disease – Microscopic Colitis
- Event Type Code 14: Possible Inflammatory Bowel Disease – no further differentiation possible
- Event Type Code 15: Probable Inflammatory Bowel Disease – no further differentiation possible
- Event Type Code 16: Definite Inflammatory Bowel Disease – no further differentiation possible
- Event Type Code 99: Not enough information to adjudicate

A table for adjudicated IBD events (event type codes 1, 2, 3, 4, 5, 6, 7, 8, 9, 11, 12, 13, 14, 15 and 16) as determined by the adjudication committee will be produced. It will summarize events determined by the adjudication committee as definite IBD (event type codes 3, 6, 9, 13, and 16), probable IBD (event type codes 2, 5, 8, 12, and 15) and possible IBD (event type codes 1, 4, 7, 11, and 14). Definite and probable IBD will also be aggregated and summarized. This table will be stratified by subjects with or without a previous medical history of IBD. Previous medical history of IBD will be determined using the information recorded on the Extra-Articular Assessment at Screening CRF page ("Does subject have a history of IBD?").

A separate table will present the adjudicated gastrointestinal events by type. For each gastrointestinal event type (17 total), the individual PTs which fall within each event type will be summarized. It will include events determined by the adjudication committee as definite IBD

probable IBD and possible IBD. It will also include events determined as Symptoms not consistent with IBD (event type code 10) and Not enough information to adjudicated (event type code 99).

A listing of all events identified for potential review by the IBD adjudication committee will be produced. This listing will indicate whether each event was escalated to the committee for formal review/adjudication.

A listing will present the adjudicated IBD events by type. For each IBD event type (event type codes 1 through 16 and 99; 17 total), the individual PTs which fall within each event type will be listed.

A third listing will present the individual diagnostic criteria met for each adjudicated IBD event.

10.2.4.7 Hypersensitivity (including Anaphylaxis)

A separate table will be prepared based on the MedDRA anaphylaxis Algorithm (see [Section 12.1](#)) for acute anaphylactic events (reported on the same day as when an injection was administered or 1 day after). An AE glossary table will also be produced to summarize the MedDRA coding for these events. The glossary table will include the following fields: reported term, PT, LLT, HLT, and SOC.

A separate table will be prepared to summarize all hypersensitivity events and serious hypersensitivity events, identified using the SMQ “Hypersensitivity (SMQ)”. All TEAEs which code to a PT included in the Scope=Narrow search will be included in this table. In addition, a separate table will be prepared to summarize serious hypersensitivity events, identified using the SMQ “Hypersensitivity (SMQ)”. All serious TEAEs which code to a PT included in the Scope=Narrow search will be included in this table. An AE glossary table will also be produced to summarize the MedDRA coding for these events. The glossary table will include the following fields: reported term, PT, LLT, HLT, and SOC.

Furthermore, a separate table will be prepared to summarize injection site reactions, identified by looking under the HLTs “Administration site reactions NEC” and “Injection site reactions”.

10.2.4.8 Hepatic events and DILI

The table for hepatic events will be created based on the SMQ of “Drug related hepatic disorders - comprehensive search (SMQ)” excluding the 2 sub-SMQs “Liver neoplasms, benign (incl cysts and polyps) (SMQ)” and “Liver neoplasms, malignant and unspecified (SMQ)”. For each of the above SMQs, include all TEAEs which code to a PT included in the Scope=Broad and/or Scope=Narrow.

Note that all AEs meeting the above criteria are to be included. It should be limited to events that the investigator determined to be related to study drug.

Also, potential Hy’s Law cases will be reported separately in a liver function test table (see [Section 10.3](#))

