 - if the month and year of the start date is the same as the month and year of first dose and the imputed stop date is before the date of first dose, then set the start date to the 1st of that month

In the event of ambiguity or incomplete data which makes it impossible to determine whether an AE is treatment emergent, the AE will be considered as treatment emergent.

Other imputations

In addition, the following will apply for presenting AE in summary tables:

- if the intensity of an AE is unknown, it will be considered as severe.
- if the relationship to study drug is missing, it will be considered as related.

For missing seriousness, no imputation rule will be applied.

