10.2.1 Standard AE summaries

Tables for incidence of the following categories of TEAES will be provided:

- TEAEs (Overview)
- TEAEs by SOC, HLT, and PT
- TEAEs by decreasing frequency of PT
- TEAEs above reporting threshold of 5% by PT, by SOC and PT
- TEAEs by maximum intensity
- TEAEs by relationship to IMP
- Related TEAEs by SOC, HLT, and PT
- Related TEAEs above reporting threshold of 5% by PT, by SOC and PT
- TEAEs leading to study discontinuation, by SOC, HLT, and PT
- TEAEs leading to study drug discontinuation, by SOC, HLT, and PT
- Treatment-emergent SAEs (TESAEs) by SOC, HLT, and PT
- TESAEs by relationship by SOC, HLT, and PT
- TEAEs leading to death by SOC, HLT, and PT - deaths will be also be tabulated and listed
- Non-Serious TEAEs above reporting threshold of 5% by relationship by PT

Some selected tables of incidence will include the exposure adjusted incidence rate (EAIR) with associated 95% confidence interval and the exposure adjusted event rate (EAER) (see [Section 10.2.3](#)). The categories of TEAEs concerned are listed below.

- TEAEs by SOC, HLT, PT,
- TEAEs leading to study discontinuation by SOC, HLT, PT,
- TEAEs leading to study drug discontinuation,
- TEAEs by timing of onset relative to ADA_b status by SOC, HLT, PT (on subjects treated with BKZ). This will include columns for the following:
 - TEAEs starting before the first ADA_b positive result (includes ADA_b categories 2 and 5) where TEAEs have occurred before the following events: a) the first positive ADA_b result for subjects in category 2 and b) the first post-Baseline boosted ADA_b titer result for subjects with titer results and the first post-Baseline positive ADA_b result for subjects with positive ADA_b at Baseline with no other samples with titer available for subjects in category 5
 - TEAEs starting on the same date or after the first ADA_b positive result (includes ADA_b Categories 2, 3, 4, 5 and 6) where TEAEs have occurred on or after the following events: a) the first positive ADA_b results for subjects in categories 2, 3, 4 and 6, and b) the first post-Baseline boosted ADA_b titer result for subjects with titer results and the first post-Baseline positive ADA_b result for subjects with positive ADA_b at Baseline with no other samples with titer available for subjects in category 5
 - TEAEs for subjects who are ADA_b negative at all timepoints (includes ADA_b Category 1)

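### The SAP gives two incompatible inclusion rules for the hepatic-event table (Section 10.2.4.8): all qualifying events, or only those the investigator judged related

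*SAP*

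**What the plan says.** Section 10.2.4.8 states four things about the content of the hepatic table, in this order.

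- The source: "The table for hepatic events will be created based on the SMQ of" drug-related hepatic disorders (comprehensive search), less two sub-SMQs for benign and for malignant or unspecified liver neoplasms.
- The scope: "For each of the above SMQs, include all TEAEs which code to a PT included in the Scope=Broad and/or Scope=Narrow".
- A reminder: "Note that all AEs meeting the above criteria are to be included".
- A restriction, immediately afterwards: "It should be limited to events that the investigator determined to be related to study drug".

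Hepatic events and DILI are on the list of safety topics in Section 10.2.4. For those topics the general rule is "The incidence of other safety topics of interest will be summarized by MedDRA system organ class, high level term, and PT", with EAIR, its 95% CI and EAER added to the tables. That general rule carries no causality condition.

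**The concern.** The third and fourth statements cannot both be carried out. An event that codes to a qualifying term but was judged unrelated must be included under one and excluded under the other.

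The choice affects what the table can show. Comparing all hepatic events between arms could reveal an excess that individual investigators had put down to comedication or other illness. A table confined to events judged related cannot. The output would also look complete under a hepatic-events title, so the filter could go unnoticed. As the text stands, the programmer settles the rule. If it is settled after treatment codes are released, either choice could look result-driven.

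**Working it through.** The SAP states no figure to reproduce. The check is a comparison of texts, followed by the effect of each reading on the two rates.

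**1. Can the sentences be reconciled?** The criteria preceding the reminder are SMQ membership, broad or narrow scope, the two excluded sub-SMQs and treatment emergence. None concerns investigator causality. The SMQ's name contains the words drug related, but the SAP applies it through coding to preferred terms, not through the causality assessment. The sentences therefore conflict.

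**2. Which sentence is out of line?**

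| Place in SAP | Rule for inclusion | Causality filter? |
|---|---|---|
| 10.2.4.1 Infections | SOC, HLGT, or sponsor search with adjudication | No |
| 10.2.4.2 Malignancies | Narrow SMQ | No |
| 10.2.4.3 MACE | Adjudication | No |
| 10.2.4.4 Neutropenia | List of PTs, serious or not | No |
| 10.2.4.5 SIB | Adjudication | No |
| 10.2.4.6 IBD | Adjudication | No |
| 10.2.4.7 Hypersensitivity | Narrow SMQ, anaphylaxis algorithm | No |
| 10.2.4.8 Hepatic, scope and reminder | SMQ, broad and narrow, all events | No |
| 10.2.4.8 Hepatic, last sentence | Related events only | Yes |

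Only the last sentence applies such a filter. Related events already have their own standard output in Section 10.2.1 ("Related TEAEs by SOC, HLT, and PT"), so the restriction fills no gap. The Amendment 1 log says that topic subsections were created and updated, and gives no reason for a related-only rule.

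**3. Which events would go?** Section 4.2.3 provides that "if the relationship to study drug is missing, it will be considered as related". Only events actively judged unrelated would be lost.

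**4. Effect on the rates (Section 10.2.3).**

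- EAER = 100 × (number of events) / (total time at risk). The filter leaves the denominator unchanged. If a share *p* of an arm's hepatic events is judged unrelated, its EAER is multiplied by (1 − *p*).
- EAIR = 100 × (subjects with an event) / (exposure, counted to the first event for those subjects and as full time at risk for the rest). The filter removes a subject from the numerator only if all of that subject's hepatic events were judged unrelated. That subject's exposure then runs for the full time at risk.
- Illustration: a subject has two hepatic events, one related and one not. Filtering cuts the event count from 2 to 1. The subject count stays at 1.

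Event loss and EAIR loss therefore need not be proportional. The SAP gives no value for *p*, which could be anything from 0 to 1 in either arm.

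**The case against.** The strongest reply is that this is a drafting slip with limited reach. Several parts of that reply stand.

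- The section says twice that everything is included, so it is not established that the plan excludes unrelated events. Any loss depends on which sentence is programmed.
- A reader might infer that the filter removes the randomised comparison of hepatic events from the report. The SAP does not support that. Sections 10.2 and 10.2.1 provide TEAEs by SOC, HLT and PT, by treatment group, with EAIR and EAER, and without a causality filter. All AEs are listed by subject.
- Liver laboratory outputs carry no causality filter. Section 10.3 tabulates transaminase, bilirubin and ALP thresholds, markedly abnormal liver enzymes and potential Hy's Law cases. It also lists hepatic events.
- A reader might also infer a bias favouring one arm. Nothing shows this. Section 4.3.1 keeps investigators blinded until the final analysis is completed, and including unrelated events can raise counts in both arms.
- Section 10.2.4 bases these analyses on a separate safety-topic specification dated April 2021, which is not at hand and may state the rule clearly.

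It could also be said that the last sentence refers to a DILI display rather than the hepatic table. The section defines no such display, so the sentence has nothing else to refer to.

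None of this removes the contradiction. Individual PT rows and listings are not the same as the pooled SMQ table by arm, and a clear external specification would not correct the SAP text.

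**Conclusion.** Section 10.2.4.8 is wrong as written: its closing restriction contradicts the two statements before it. The reading that fits the rest of the SAP is full inclusion. That a *not* was dropped is probable but remains an inference.

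If the restriction is programmed literally, the consequence is confined to one descriptive output, the only pooled hepatic SMQ table with incidence, EAIR and EAER by arm. No hypothesis test is affected. The number of events at stake cannot be stated from the document, and neither can the direction of any change in the comparison between arms.

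**What to change.** In the last sentence of that note in Section 10.2.4.8, insert *not* so that it reads as should not be limited to related events. The table then holds all TEAEs in the SMQ, broad and narrow, less the two liver-neoplasm sub-SMQs. If the causality view is wanted, add related events as a sub-row within the same table.

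Check the table shell and the April 2021 safety-topic specification against the corrected sentence. Do this before the lock for the Week 16 interim analysis, when sponsor personnel receive the treatment codes.

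The cost is one word in the SAP and a check of the programming. Hepatic counts may be higher than under the literal reading, potentially in both arms.

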10.2.5 COVID-19 impact

To assess the impact of COVID-19 pandemic on safety, additional summaries and listings will be presented.

For reporting purposes, AEs will be assigned to either Pre-COVID-19, COVID-19, or post-COVID-19 pandemic period by comparing the AE start date (based on imputed date) to the COVID-19 pandemic period dates (AE allocated to a period if it starts during the period):

The following categories of TEAEs will be summarized by MedDRA SOC, HLT and PT, including EAIR and EAER.

- All TEAEs by time of onset relative to COVID-19 pandemic period (pre – during – post) by region and overall,
- All TEAEs leading to study discontinuation and/or permanent withdrawal of study medication by time of onset relative to COVID-19 pandemic period (pre – during – post) by region and overall,
- All Serious TEAEs by time of onset relative to COVID-19 pandemic period (pre – during – post) by region and overall,
- All COVID-19 related TEAEs by treatment group, by region and overall – COVID-19 related TEAEs will be identified by the two preferred terms “Corona virus infection” and “coronavirus test positive” and will include confirmed or suspected COVID-19 infections.

A listing of COVID-19 related AEs will be presented where these AEs are identified as described above. Additionally, the listing of AEs will include a column for COVID-19 relatedness and the time of onset of each AE relative to the COVID-19 pandemic will be included in all AE listings.

For the purpose of calculating EAIR and EAER by COVID-19 pandemic period, the calculation of exposure time at risk presented in [Section 10.1.2](#) will be used. An individual subject may therefore be counted in the denominator for several COVID-19 pandemic periods dependent on whether the subject is still considered at risk on the COVID-19 pandemic start and stop dates. In this case time at risk will be calculated separately for each period.

10.3 Clinical laboratory evaluations

The list of the laboratory measurements/variables that will be evaluated in the study is specified in [Table 10–2](#) per laboratory category.

Table 10–2: Laboratory measurements

Hematology	Biochemistry	Urinalysis
Basophils	Calcium	pH
Eosinophils	Chloride	Albumin (protein)
Lymphocytes	Magnesium	Glucose
Monocytes	Potassium	Blood
Neutrophils	Sodium	Leukocyte esterase
Hematocrit	Glucose	Nitrite
Hemoglobin	BUN	Urine dipstick for pregnancy testing ^b
MCH	Creatinine	Urine drug screen ^c
MCHC	hs-CRP	
MCV	AST	

Hematology	Biochemistry	Urinalysis
Platelet count	ALT	
RBC count	GGT	
WBC count	ALP	
	Total bilirubin	
	Triglycerides ^a	
	Cholesterol ^a	
	HDL cholesterol ^a	
	LDL cholesterol ^a	
	LDH	
	Serum pregnancy testing ^b	

ALP=alkaline phosphatase; ALT=alanine aminotransferase; AST=aspartate aminotransferase; BUN=blood urea nitrogen; CRP=C-reactive protein; ET=early termination; GGT=gamma-glutamyltransferase; HDL=high density lipoprotein, IMP=investigational medicinal product; LDH=lactate dehydrogenase; MCH=mean corpuscular hemoglobin; MCHC=mean corpuscular hemoglobin concentration; MCV=mean corpuscular volume; RBC=red blood cell; SFU=Safety Follow-Up; WBC=white blood cell.

^a Biochemistry will include triglycerides, cholesterol, HDL cholesterol, and LDL cholesterol at Baseline, Weeks 12 and 24, and at the ET Visit.

^b Pregnancy testing will consist of serum testing at the Screening Visit for all women of childbearing potential. The pregnancy test will be urine at all other visits.

^c Urine drug screen will be performed at Screening Visit.

Biochemistry and hematology values will be flagged based on their reference range:

- Values that are below the lower limit of the reference range will be flagged as ‘L’ (low)
- Values that are above the upper limit of the reference range will be flagged as ‘H’ (high)
- All other values will be referenced as normal.

Markedly abnormal values for blood chemistry and hematology will be defined as laboratory values graded 3 or 4 according to the Rheumatology Common Toxicity Criteria (RCTC).

Definitions of the markedly abnormal values are given in [Table 10–3](#) and [Table 10–4](#) and are based on the RCTC units. All units in the tables below will be converted to the standard units based on Clinical Data Interchange Standards Consortium (CDISC) standards.

Table 10–3: Definitions of markedly abnormal biochemistry values

Parameter name	Unit	Criteria	Abnormal designation
Creatinine	mmol/L	>3.0 x ULN or >3.0 x Baseline	AH
Glucose	mmol/L	<2.2 >13.9	AL AH
Calcium	mmol/L	>3.1 <1.75	AH AL

Parameter name	Unit	Criteria	Abnormal designation
Magnesium	mmol/L	>1.23	AH
		<0.4	AL
Potassium	mmol/L	>6.0	AH
		<3.0	AL
Sodium	mmol/L	>155	AH
		<130	AL
Triglyceride	mmol/L	>5.7	AH
Cholesterol	mmol/L	>10.34	AH

AH=abnormal high; AL=abnormal low; dL = deciliter; L = liter;
mg = milligram; mmol = millimoles; ULN = upper limit of normal.

Table 10–4: Definitions of markedly abnormal hematology values

Parameter name	Unit	Criteria	Abnormal Designation
Hemoglobin	g/L	<80	AL
		>40 above ULN or >40 above Baseline if Baseline is above ULN	AH
Lymphocytes Absolute	10 ⁹ /L	<0.5	AL
		>20.0	AH
Neutrophils Absolute	10 ⁹ /L	<1.0	AL
Platelets	10 ⁹ /L	<50	AL
WBC/ Leukocytes	10 ⁹ /L	<2.0	AL
		>100	AH

Definitions of the markedly abnormal values for liver enzyme elevation are given in [Table 10–5](#).

Table 10–5: Definitions of markedly abnormal liver enzyme elevation values

Parameter name	Unit	Criteria	Abnormal Designation
Alkaline Phosphatase		>5.0 x ULN	AH
ALT	U/L	>5.0 x ULN	AH
AST	U/L	>5.0 x ULN	AH
Total Bilirubin	umol/L	>3.0 x ULN	AH
GGT	U/L	>5.0 x ULN	AH

ALT= alanine aminotransferase; AST = aspartate aminotransferase; GGT=gamma-glutamyltransferase.

All laboratory summaries will be presented in standard international (SI) units and will be based on observed case values. In the case where laboratory values are below the lower limit of quantification, then these will be set to the midpoint between 0 and the lower limit of quantification for the purpose of summarizing the data.

In the case where laboratory data are expressed as above a fixed value (ie, “>xx.xx”), then the numeric portion of the value will be used (ie, : xx.xx) to present and calculate statistics.

To define the minimum/maximum post-Baseline values, all post-Baseline assessments including those at unscheduled visits (but excluding any that occur more than 140 days after the last administration of study medication) will be used.

Different summary tables for hematology, biochemistry variables (except hs-CRP which will be analyzed in the efficacy section) and urinalysis (pH, Albumin (protein), glucose, blood, leukocyte esterase and nitrite) will be provided in the SS. For shift tables, results for the treatment period will be presented together for the overall study period.

As indicated in [Section 3.1](#), for tables where data are summarized by visit only values occurring at scheduled visits will be included.

For each laboratory parameter, the below results will be presented for the overall study period, by treatment group:

- Observed values at Baseline and observed values and changes from Baseline at each scheduled post-Baseline visit.
- Number and percentage of subjects by CTCAE grade (version 4.03) (when applicable) based on the minimum/maximum post-Baseline value (for blood chemistry and hematology).
- Shift in CTCAE grade from Baseline to minimum/maximum post-Baseline (for blood chemistry and hematology). Subjects who meet the decreased potassium criterion of 3.0-<LLN, which is specified as the decreased potassium lab criterion for both CTCAE Grade 1 and Grade 2, will be counted as Grade 2.
- Number and percentage of subjects meeting the below criteria at any time during the study:
 - AST: >2xULN, >3xULN, >5xULN, >10xULN, >20xULN

- ALT: >2xULN, >3xULN, >5xULN, >10xULN, >20xULN
- AST or ALT: >2xULN, >3xULN, >5xULN, >10xULN, >20xULN
- Bilirubin: >1xULN, >1.5xULN
- ALP: >2xULN
- Number and percentage of subjects with potential Hy's Law cases based on the two following definitions:
 - [AST \geq 3xULN or ALT \geq 3xULN] and Total Bilirubin \geq 2xULN
 - [AST \geq 3xULN or ALT \geq 3xULN] and Total Bilirubin \geq 2xULN in the absence of ALP \geq 2xULN

In order to meet either of the above criteria, a subject must experience the elevation in bilirubin and ALT or AST (and the absence of ALP elevation, if applicable) at the same visit.

The below results will be presented on the SS. All values observed at any time while on treatment (ie, occurring at scheduled and unscheduled visits) will be included in the below tables. Baseline values and values observed more than 140 days after the last administration of study medication are not considered:

- Number and percentage of subjects with treatment emergent markedly abnormal laboratory data overall (for blood chemistry and hematology). All values observed at any time while on treatment (ie, occurring at scheduled and unscheduled visits) will be included in this table summarizing markedly abnormal values. For this summary, Baseline values and values observed more than 140 days after the last administration of study medication are not considered.
- Number and percentage of subjects with markedly abnormal liver enzyme elevation tests (data beyond the CTCAE Grade 3 thresholds as outlined in [Table 10–5](#))

All laboratory data will be listed by treatment, subject and visit including changes from Baseline for numeric variables, flags for measurements outside the normal ranges, the relative study day, a flag for whether the test was not done and a flag for whether the subject was fasting.

The markedly abnormal laboratory data will also be listed separately.

Listings will include Hepatitis B and C, human immunodeficiency virus (HIV), genomic proteomic/metabolomics, and genetic/epigenetic tests.

In addition, the laboratory results classified as Grade 3 or Grade 4 will be listed separately.

Urinalysis laboratory results and hepatic events will be listed separately.

